- Peripheral blast count before conditioning for the first HSCT after the start of this drug [≤ 1000 /µL, > 1000 /µL, not performed]
- Myeloblast count before conditioning for the first HSCT after the start of this drug [≤ 50%, > 50%, not performed]
- Time from the date of final dose of this drug to the date of the first HSCT after the start of this drug [< 4 weeks, ≥ 4 weeks to < 8 weeks, ≥ 8 weeks to < 12 weeks, ≥ 12 weeks to < 16 weeks, ≥ 16 weeks]
- Treatment cycles [1 cycle, 2 cycles, 3 cycles, 4 cycles, 5 cycles, 6 cycles, > 6 cycles]
- Treatment cycles [≤ 3 cycles, ≥ 4 cycles]
- Dosing of > 1.8 mg/m^2 per cycle [absent, present] (Considered to be present, if there is a cycle of > 1.8 mg/m^2 per cycle during the treatment period.)
- Pregnancy [absent, present] \* Pregnancy during the treatment period. Limited to cases in which information on pregnancy is collected
- Best overall response [complete remission (CR) or complete remission with incomplete hematologic recovery (CRI), progression or relapse, indeterminate/other, not performed]
- Minimal residual disease (MRD) [negativity achieved, negativity not achieved, test not performed]
  - \* Irrespective of the result of best overall response.
- Best overall response and MRD [CR/CRI achieved and negativity achieved, CR/CRI achieved and negativity not achieved, progression/relapse and negativity achieved, progression/relapse and negativity not achieved] \* "Indeterminate/other" and "not performed" are excluded.
- Adverse drug reactions that occurred during the treatment period - liver disorder as a safety specification [absent, present]

Subgroup analyses of hematologic response and MRD will be performed for the following patient characteristics and other factors:

- Age [< 15 years, ≥ 15 to < 65 years, ≥ 65 years]
- Age [< 18 years, ≥ 18 to < 55 years, ≥ 55 years]
- Age [< 15 years, ≥ 15 to < 40 years, ≥ 40 years]
- Disease name [Relapsed CD22+ acute lymphocytic leukemia (ALL), refractory CD22+ ALL]
- Chromosome karyotype [normal, t (4;11), unknown]
- Chromosome karyotype [Philadelphia chromosome positive, negative, unknown]\* Philadelphia chromosome is considered positive if the chromosome karyotype is t(9;22).
- Hemoglobin level immediately before the start of this drug [< 10 g/dL, ≥ 10 g/dL, not performed]
- Platelet count immediately before the start of this drug [< 10 × 10^4/µL, ≥ 10 × 10^4/µL, not performed]

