#### 6.4. Covariates

Potential risk factors identified from available data including those from clinical studies conducted to date that are associated with development of liver disorders including VOD/SOS as safety specification include:

- Past history of hepatitis or hepatic disease

- Presence/absence of hepatic impairment
- Peripheral blast count immediately before the start of this drug
- ECOG PS before the start of this drug
- Salvage line of the induction treatment with this drug
- Number of treatment cycles of this drug
- HSCT status (performed or not performed)
- Peripheral blast count before conditioning for HSCT

Potential risk factors associated with the occurrence of safety specification events of VOD/SOS include:

- Age
- Past history of hepatitis or hepatic disease
- Platelet count immediately before the start of this drug
- Salvage line of the induction treatment with this drug
- Number of treatment cycles of this drug
- HSCT status (performed or not performed)
- Conditioning with alkylating agents or busulfan
- Total bilirubin, AST, and ALT levels before conditioning for HSCT

Potential prognostic factors associated with achieving hematologic remission include:

- Age
- ALL Status (relapsed or refractory)
- Chromosome karyotype
- Hemoglobin, platelet count, peripheral blast count, and myeloblast count immediately before the start of this drug
- Salvage line of the induction treatment with this drug
- HSCT status (performed or not performed)

Potential prognostic factors associated with overall survival include:

- Age
- ALL Status (relapsed or refractory)
- Chromosome karyotype
- Hemoglobin, platelet count, peripheral blast count, and myeloblast count immediately before the start of this drug
- Salvage line of the induction treatment with this drug
- HSCT status (performed or not performed)
- Hematologic response, MRD

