- Medical history (past) - Hepatitis or hepatic disease
- Medical history (present) - Hepatitis or hepatic disease
- AST and ALT levels immediately before the start of this drug

- $\gamma$ -GTP level immediately before the start of this drug
- Salvage line of the induction treatment with this drug
- HSCT before the start of this drug

Similar analysis will be performed for patients aged < 15 years in the patient population aged < 65 years.

- **Status of the treatment with this drug**

For the SAS, status of the treatment with this drug will be summarized with respect to the following factors. Similar summaries will also be performed by absence/presence of HSCT after the start of this drug:

- Number of treatment cycles (continuous)
- Number of treatment cycles [1 cycle, 2 cycles, 3 cycles, 4 cycles, 5 cycles, 6 cycles, > 6 cycles]
- Number of treatment cycles [ $\leq$  3 cycles,  $\geq$  4 cycles]
- Dose amount in each cycle (continuous)
- Total dose amount (continuous)
- Dosing of  $> 1.8 \text{ mg/m}^2$  per cycle [absent, present] (Considered to be present, if there is a cycle of  $> 1.8 \text{ mg/m}^2$  per cycle during the treatment period.)

- **Pregnancy**

For the SAS, pregnancy status will be summarized:

- Pregnancy [absent, present] \* Pregnancy during the treatment period. Limited to cases in which information on pregnancy is collected

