**Exploration of factors associated with the occurrence of VOD/SOS (subgroup analyses):** Patients who experienced VOD/SOS after the start of this drug and patients who experienced VOD/SOS with HSCT performed after the start of this drug will be summarized in terms of n and proportion by each of the following factors selected from those specified in Section 5.4. In addition, risk ratios for the proportion of patients with the AR for different subgroups will be determined as per Section 8.1.3 and presented graphically. If, however, there is a category with less than 10 patients and after reconsideration it is considered difficult to determine the risk ratio for the category, it will not be determined for the relevant category. To investigate correlation between factors and occurrence of the ADR, statistical tests specified in Section 8.1.3 will be performed.

- Age [ $< 15$  years,  $\geq 15$  to  $< 65$  years,  $\geq 65$  years]
- Age [ $< 18$  years,  $\geq 18$  to  $< 55$  years,  $\geq 55$  years]
- Age [ $< 15$  years,  $\geq 15$  to  $< 40$  years,  $\geq 40$  years]
- Hepatic impairment
- Medical history (past) - VOD/SOS
- Medical history (past) - Hepatitis or hepatic disease
- Medical history (present) - VOD/SOS
- Medical history (present) - Hepatitis or hepatic disease
- ECOG PS before the start of this drug [ $0, 1, \geq 2$ , not performed]
- AST and ALT levels immediately before the start of this drug
- $\gamma$ -GTP level immediately before the start of this drug
- Total bilirubin level immediately before the start of this drug
- Platelet count immediately before the start of this drug
- Peripheral blast count immediately before the start of this drug
- Salvage line of the induction treatment with this drug
- HSCT before the start of this drug
- HSCT after the start of this drug

Similarly, VOD/SOS that occurred with HSCT performed after the start of this drug will be analyzed with respect to the following factors:

- Type of the first HSCT after the start of this drug
- Donor of the first HSCT after the start of this drug
- Conditioning with alkylating agent for the first HSCT after the start of this drug
- Conditioning with busulfan for the first HSCT after the start of this drug

- ECOG PS before conditioning for the first HSCT after the start of this drug [0, 1, ≥ 2, not performed]
- AST and ALT levels before conditioning for the first HSCT after the start of this drug

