- γ-GTP level before conditioning for the first HSCT after the start of this drug
- Total bilirubin level before conditioning for the first HSCT after the start of this drug
- Platelet count before conditioning for the first HSCT after the start of this drug
- Peripheral blast count before conditioning for the first HSCT after the start of this drug
- Time from the date of final dose of this drug to the date of the first HSCT after the start of this drug
- Treatment cycles [1 cycle, 2 cycles, 3 cycles, 4 cycles, 5 cycles, 6 cycles, > 6 cycles]
- Treatment cycles [< 3 cycles, ≥ 4 cycles]

Listings that account for the occurrence of VOD/SOS and other features in patients who experienced VOD/SOS will be prepared.

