- Myeloblast count before conditioning for the first HSCT after the start of this drug
- Time from the date of final dose of this drug to the date of the first HSCT after the start of this drug
- Treatment cycles [1 cycle, 2 cycles, 3 cycles, 4 cycles, 5 cycles, 6 cycles,  $> 6$  cycles]
- Treatment cycles [ $\leq 3$  cycles,  $\geq 4$  cycles]
- Best overall response
- MRD
- Best overall response and MRD
- Adverse drug reactions that occurred during the treatment period - liver disorder as a safety specification

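### In the post-HSCT VOD/SOS factor list of SAP 8.2.3.1, the two-level treatment-cycle factor has no category for patients with exactly 3 cycles and conflicts with Section 5.4

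*SAP*

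**What the plan says.** SAP 8.2.3.1 sets out an exploration of factors associated with VOD/SOS. Patients with the event are summarized "by each of the following factors selected from those specified in Section 5.4", with risk ratios, a graph and tests. A second list follows for transplanted patients: "Similarly, VOD/SOS that occurred with HSCT performed after the start of this drug will be analyzed with respect to the following factors". It ends with two versions of the cycle factor. The first is "Treatment cycles [1 cycle, 2 cycles, 3 cycles, 4 cycles, 5 cycles, 6 cycles, > 6 cycles". The second is "Treatment cycles [< 3 cycles, ≥ 4 cycles".

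Section 5.4 defines the two-level factor as "Treatment cycles [≤ 3 cycles, ≥ 4 cycles". The treatment-status summary in 8.2.2 and the early-death factor list in 8.2.3.3 use the same ≤ 3 / ≥ 4 split. Section 6.4 includes "Number of treatment cycles of this drug" among the potential risk factors for VOD/SOS.

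**The concern.** Cycle counts are whole numbers, so the printed brackets leave a hole at 3. This is an operative instruction: it fixes which patients enter a risk ratio, its graph and a test for a factor that Section 6.4 names in advance. Evaluating VOD/SOS risk factors is also the stated basis of the sample size (Protocol 8.10.2).

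If the line is programmed literally, three things follow:
- Patients with 3 cycles, and any VOD/SOS events among them, drop out of this comparison.
- The VOD/SOS and early-death tables carry nearly identical labels but use different low-exposure groups.
- The Section 9 listing of patients with VOD/SOS takes its risk factors from this list, so a 3-cycle case would have no two-level category there.

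**Working it through.** **1. The plan's own figure.** The only stated number related to this analysis is the power in Protocol 8.10.2 and SAP 2.1. Inputs: 176 patients split 1:1, so n = 88 per group; p1 = 0.185; p2 = 0.062; two-sided significance level 0.1 (z = 1.645). With a pooled-variance normal approximation and no continuity correction:

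power = Φ{ [ |p1 − p2|·√n − z·√(2·p̄·(1 − p̄)) ] / √(p1(1 − p1) + p2(1 − p2)) }, where p̄ = (p1 + p2)/2.

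- p̄ = 0.1235
- Numerator: 0.123 × √88 − 1.645 × √0.2165 = 1.154 − 0.765 = 0.389
- Denominator: √(0.1508 + 0.0582) = 0.457
- Power = Φ(0.85) = 80.2%

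With the less rounded rates 18.45% and 6.15%, the same formula gives 80.4%, the stated value. Neither the cycle factor nor its grouping enters this calculation, so the figure stands whichever sign is right.

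**2. Coverage of each grouping.** Each possible cycle count is set against each printed grouping:

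| Cycles | 8.2.3.1, two-level (< 3, ≥ 4) | 5.4, 8.2.2, 8.2.3.3 (≤ 3, ≥ 4) | 8.2.3.1, seven-level |
|---|---|---|---|
| 1 | low | low | 1 |
| 2 | low | low | 2 |
| 3 | **none** | low | 3 |
| 4 | high | high | 4 |
| 5 | high | high | 5 |
| 6 | high | high | 6 |
| more than 6 | high | high | > 6 |

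Exactly one count, 3 cycles, is unassigned, and only in the two-level factor of 8.2.3.1.

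**3. Where the factor applies.** It stands in the sub-list for VOD/SOS with HSCT after the start of the drug. The preceding list in 8.2.3.1 contains no cycle factor and is unaffected.

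**4. Number omitted.** This equals (number of patients with HSCT after the start of the drug) × (share of them with exactly 3 cycles). Neither document gives either term, so no count can be derived.

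**5. Effect on the contrast.** Let e12/n12 be the VOD/SOS proportion in patients with 1 or 2 cycles, and e3/n3 the proportion in those with 3. The low group's proportion is e12/n12 as printed and (e12 + e3)/(n12 + n3) under Section 5.4. The two agree only if e3/n3 = e12/n12. With the low group as denominator, the printed version gives the larger risk ratio if e3/n3 is the higher of the two and the smaller risk ratio if it is the lower. The documents do not say which holds.

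**The case against.** **Section 5.4 already governs.** The factors are said to come from Section 5.4, which contains no < 3 / ≥ 4 factor. A careful programmer would build one cycle variable from 5.4 and reuse it. This shows which grouping was meant and makes a literal reading less likely. It does not remove the conflict, because 8.2.3.1 spells out its own categories and a program checked against that line would be accepted with the gap.

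**The sign may be an artefact of reading the PDF.** The point turns on one glyph. Section 5.4 marks reference categories by underlining, which is easily confused with the bar of ≤. Other inequality signs in the SAP also look unreliable: Section 5.4 has white cells as both ≤ 4000 and ≥ 4000, and 8.2.3.3 has an age band starting at > 15 where other lists have ≥ 15. This objection stands as a reason to check the source. Against it, ≥ 4 is intact on the same line, and ≤ 3 appears in all three other places. If the source shows ≤, the point falls away.

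**The 3-cycle patients are not lost.** A reader might infer that the whole VOD/SOS exploration leaves them out. It does not: the seven-level factor immediately above has a 3-cycle level and receives the same risk ratios and tests. What remains is that 8.2.3.1 allows a risk ratio to be omitted for a category with fewer than 10 patients. Seven levels within transplanted patients are more exposed to that rule than two, so the two-level factor is not redundant.

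**The analysis is exploratory.** SAP 4.1 treats p-values as descriptive and sets no significance level. That limits the consequence to the content of one comparison.

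**Conclusion.** The gap and the conflict with Section 5.4 hold on the text of the SAP, subject to confirming the sign in the source. The size is small: one two-level, exploratory comparison in the post-HSCT sub-list, plus the matching entry in the VOD/SOS listing. Sample size, stated power, endpoints and analysis sets do not change.

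Two stronger readings are not supported. A reader might attach a number of lost patients and events, but the documents give neither the number of HSCT recipients nor the distribution of cycles. A reader might also infer that dropping the 3-cycle group exaggerates the contrast between low and high exposure. That requires VOD/SOS risk to be higher at 3 cycles than at 1 or 2; Section 6.4 calls the number of cycles only a potential risk factor and gives no direction.

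The correction is still worth making, because the intended grouping is evident and the line directs an analysis of a pre-named factor.

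**What to change.** Confirm the sign in the source SAP. If it is <, change the two-level factor in 8.2.3.1 to ≤ 3 cycles versus ≥ 4 cycles, matching Sections 5.4, 8.2.2 and 8.2.3.3. Check that the program for the VOD/SOS tables, and for the Section 9 listing that draws on the same factors, uses that grouping. This is an analysis category and has no bearing on treatment. It costs one character in the SAP and a brief check of the program, with no new data.

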#### 8.2.3.2. Adverse events

- **Serious and non-serious adverse events**

The number (n) and proportion of patients with serious adverse events (SAEs) will be tabulated by SOC and PT. Similar summary will also be performed for non-serious adverse events (AEs), but a threshold will be set for the proportion as necessary, and summary will be performed only for events that are associated with a proportion at or above the threshold.

#### 8.2.3.3. Other endpoints

- **Death after HSCT**

To investigate early deaths after HSCT (see Section 6.1 for definition), the following kinds of patient data will be summarized as per Section 8.1.2. The denominator of a proportion is the number of patients included in the 1-step higher itemization level.

- Patients in the SAS who underwent HSCT after the start of this drug and have finished the survey (Patients who are recorded as discontinued in the "Record of continued/discontinued survey [treatment period]" in the case report form or patients for whom "Record of continued/discontinued survey [follow-up period]" in case report form is filled in. The latter means the survey is discontinued and completed for the patient.)
  - Death after HSCT
    - ◊ Death within 100 days post-HSCT
    - ◊ Death after > 100 days post-HSCT
    - ◊ Transplant-related death (non-relapse death)
      - Death within 100 days post-HSCT
      - Death after > 100 days post-HSCT
    - ◊ Transplant-unrelated death (relapse death)
      - Death within 100 days post-HSCT
      - Death after > 100 days post-HSCT

- Survival confirmed at the time of discontinuation of the survey
- **Mortality after HSCT**

Time to death after HSCT, time to transplant-related death after HSCT, and time to transplant-unrelated death after HSCT (see Section 6.1 for definitions) will be analyzed as per Section 8.1.4 (Although the time to death after HSCT does not have any competing risk, the same analysis with competing risks will be performed for the variable). Those who included in the analysis are patients in the SAS who underwent HSCT after the start of this drug and finished the survey (Patients who are recorded as discontinued in the "Record of continued/discontinued survey [treatment period]" in the case report form or patients for whom "Record of continued/discontinued survey [follow-up period]" in case report form is filled in. The latter means the survey is discontinued and completed for the patient.). The cumulative incidence will be estimated at Week 4, Week 8, Week 12, Day 100, Week 24, Week 36, Week 48, Week 52, Week 78, and Week 104.

- **Exploration of factors associated with early death after HSCT (subgroup analyses)**

Patients with early death after HSCT will be summarized in terms of n and proportion by each of the following factors selected from those specified in Section 5.4. In addition, risk ratios for the proportion of patients who died for different subgroups will be determined as per Section 8.1.3 and presented graphically. If, however, there is a category with less than 10 patients and after reconsideration it is considered difficult to determine the risk ratio for the category, it will not be determined for the relevant category. To investigate correlation between factors and death, statistical tests specified in Section 8.1.3 will be performed. Similar analyses will also be performed for early transplant-related death after HSCT (non-relapse death).

- Age [< 15 years, > 15 to < 65 years, ≥ 65 years]
- Age [< 18 years, ≥ 18 to < 55 years, ≥ 55 years]
- Age [< 15 years, ≥ 15 to < 40 years, ≥ 40 years]
- Disease name
- Chromosome karyotype [normal, t (4;11)]
- Chromosome karyotype [Philadelphia chromosome positive, negative] \* Philadelphia chromosome is considered positive if the chromosome karyotype is t(9;22).
- Hepatic impairment
- Medical history (past) - VOD/SOS
- Medical history (past) - GVHD
- Medical history (past) - Hepatitis or hepatic disease
- Medical history (present) - VOD/SOS
- Medical history (present) - GVHD
- Medical history (present) - Hepatitis or hepatic disease
- ECOG PS before the start of this drug [0, 1, ≥ 2, not performed]
- Hemoglobin level immediately before the start of this drug
- Platelet count immediately before the start of this drug
- Peripheral blast count immediately before the start of this drug

- Myeloblast count immediately before the start of this drug
- Salvage line of the induction treatment with this drug
- HSCT before the start of this drug
- Type of the first HSCT after the start of this drug
- Donor of the first HSCT after the start of this drug
- Conditioning with alkylating agent for the first HSCT after the start of this drug
- Conditioning with busulfan for the first HSCT after the start of this drug
- ECOG PS before conditioning for the first HSCT after the start of this drug [0, 1,  $\geq 2$ , not performed]
- Hemoglobin level before conditioning for the first HSCT after the start of this drug
- Platelet count before conditioning for the first HSCT after the start of this drug
- Peripheral blast count before conditioning for the first HSCT after the start of this drug
- Myeloblast count before conditioning for the first HSCT after the start of this drug
- Time from the date of final dose of this drug to the date of the first HSCT after the start of this drug
- Treatment cycles [1 cycle, 2 cycles, 3 cycles, 4 cycles, 5 cycles, 6 cycles,  $> 6$  cycles]
- Treatment cycles [ $\leq 3$  cycles,  $\geq 4$  cycles]
- Best overall response
- MRD
- Best overall response and MRD
- Adverse drug reactions that occurred during the treatment period - liver disorder as a safety specification

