8.7. Observation Period

Observation period: The observation period will be 52 weeks for patients not undergoing HSCT within 52 weeks after the start of BESPONSA treatment or until 52 weeks following HSCT for patients undergoing it within 52 weeks after the start of BESPONSA treatment. For a patient starting BESPONSA treatment before 30 April 2020 who is transferred to another hospital during the observation period, the conclusion of the agreement on the implementation of this investigation should be requested to the hospital to which the patient has been transferred, and data from there should be collected to the extent possible.

(1) Treatment phase

From treatment initiation to Day 28 post-treatment: Safety (e.g., AEs) and efficacy (hematologic remission and survival)

(2) Follow-up phase

From Day 29 post-treatment to Week 52 (patients who did not undergo HSCT before Week 52) or 52 weeks after HSCT (patients who underwent HSCT before Week 52): Safety (VOD/SOS) and efficacy (survival)

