8.8.12. Confirmation of Survival

The following information will be entered to assess the overall survival during a period from the start date of BESPONSA treatment to the end date of the observation period:

Result of confirmation of survival at the end of the observation period, date of confirming the survival status if the patient is alive, date of death if the patient died (when the date of death is unknown, the last date of confirming survival), reason for death

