8.11.3. Data Collection Method

In this investigation, data will be entered in CRFs and evaluated using the EDC system for collecting post-marketing drug investigation data (hereinafter referred to as the system) on the Internet supplied by the sponsor. However, only when the EDC system cannot be used at the sites due to compelling reasons, data will be collected using paper CRFs. The investigator will complete CRFs within the investigation period after the end of the observation period for each booklet and submit them to the sponsor.

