## 2.1. Study Design

- **Target population**

*All patients who received this drug will be included in this survey.*

- **Survey period**

*The scheduled periods of this survey are as follows:*

*Survey period: From the date of launch of this drug to 5 years\**

*Registration period: From the date of launch of this drug to the time of lifting of approval conditions for all-case survey\**

*\*: Patients who started to receive this drug on or after May 1, 2020 will only be registered.*

The protocol may be changed to terminate the registration only period, but this change will not affect the SAP.

- **Observation period**

*Observation period: The observation period is to be 52 weeks for patients who did not undergo hematopoietic stem cell transplant (HSCT) within 52 weeks after the start of the treatment with this drug and up to 52 weeks after HSCT for patients who underwent HSCT within 52 weeks after the start of this drug. If patients who started to receive this drug on or before April 30, 2020 are transferred to another hospital during the observation period, the transferred hospitals will be requested to conclude a contract for the conduct of this survey, and the information at the transferred hospitals will be collected as much as possible.*

*[1] Treatment Period*

*From the start of treatment to Day 28 post-final dose: For assessments of safety (e.g., adverse events) and effectiveness (hematologic response, survival time)*

*[2] Follow-up period*

*For 52 weeks from 29 days after the final dose (for patients who did not undergo HSCT by 52 weeks after the start of treatment) or for 52 weeks after HSCT (for patients who underwent HSCT by 52 weeks after the start of treatment): For assessments of safety (VOD/SOS) and effectiveness (survival time)*

The starting point for the 52 week follow-up after HSCT is the day of the last HSCT performed within 52 weeks after the start of this drug.

- **Safety specification**

See Protocol Section 7.1.

- **Sample size and its rationale**

*Of the patients who have received this drug, a total of 176 patients with relapsed or refractory CD22 positive (CD22+) acute lymphocytic leukemia (ALL) will be included in the safety analysis set. In consideration of dropouts during the survey, 200 patients will be registered.*

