## 6. ENDPOINTS AND COVARIATES

### 6.1. Safety Endpoints

- Adverse events: All undesirable or unintended signs or symptoms that occurred after administration of this drug, regardless of causal relationship
- Adverse drug reactions: Adverse events assessed as causally related to this drug by the physician

- Serious adverse events or serious adverse drug reactions: Adverse events or adverse drug reactions assessed as serious by the physician

- Death after HSCT:

- Time to death after HSCT: Days and weeks from the date of first HSCT after the start of this drug to the date of death
- Event: Death (for any cause)
- Censoring: The patient is confirmed alive at the time of completion or discontinuation of the survey. The endpoint will be censored on the day when patient's survival was last confirmed.

Early death after HSCT is defined as the above event that occurred within 100 days after the first HSCT after the start of this drug. Early death is supposed to be absent if the patient died on 101 days or later, or was confirmed alive at the time of completion/discontinuation of the survey.

- Transplant-related death after HSCT (non-relapse death):

- Time to transplant-related death after HSCT: Days and weeks from the date of first HSCT after the start of this drug to the date of death.
- Event: Death due to non-tumor-related causes, resulting from worsening of the target disease of this drug
- Competing risks: Death due to tumor-related causes, resulting from worsening of the target disease of this drug
- Censoring: The patient is confirmed alive at the time of completion or discontinuation of the survey. The endpoint will be censored on the day when patient's survival was last confirmed.

Early transplant-related death after HSCT (non-relapse death) is defined as the above event that occurred within 100 days after the first HSCT after the start of this drug. Early death is supposed to be absent if the patient died on 101 days or later, or was confirmed alive at the time of completion/discontinuation of the survey.

- Transplant-unrelated death after HSCT (relapse death):

- Time to transplant-unrelated death after HSCT: Days and weeks from the date of first HSCT after the start of this drug to the date of death.
- Event: Death due to tumor-related causes, resulting from worsening of the target disease of this drug
- Competing risks: Death due to non-tumor-related causes, resulting from worsening of the target disease of this drug

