- Type of HSCT before the start of this drug (regardless of the number of HSCTs) [autologous transplant, allogeneic hematopoietic stem cell transplant with myeloablative conditioning, allogeneic hematopoietic stem cell transplant with nonmyeloablative conditioning, unknown]
- Type of the HSCT immediately before the start of this drug [same as above]
- Type of the conditioning drug for HSCT before the start of this drug (regardless of the number of HSCTs) [busulfan (BSF, BUS), cyclophosphamide (CPA), melphalan (LPAM), cytarabine (Ara-C), fludarabine phosphate (F-ara-AMP), etoposide (ETP, VP-16), other]
- Type of the conditioning drug for the HSCT immediately before the start of this drug [same as above]
- Time from the date of the HSCT immediately before the start of this drug to the date of the start of this drug (continuous)

Listings will also be prepared.

For the SAS and EAS, patients falling into the following categories defined for remission induction therapies performed before the start of this drug will be summarized in terms of n and proportion. Note that only patients who received remission induction therapy before the start of this drug will be included in this summary, except for "Remission induction chemotherapy before the start of this drug [not performed, performed]":

- Remission induction chemotherapy before the start of this drug [not performed, performed]

- Induction chemotherapy regimen and response before the start of this drug (regardless of line of therapy)
- Regimen of the induction chemotherapy immediately before the start of this drug (by line of treatment)
- Regimen and response of the induction chemotherapy immediately before the start of this drug

For the SAS and EAS, summary will be performed for anti-malignant tumor agents (drug code 42x) started by the day of the final dose of this drug that are recorded as concomitant anti-malignant tumor agents used for the target disease. Listings will also be prepared.

For the SAS and EAS, patients falling into the following categories defined for HSCT performed after the start of this drug will be summarized in terms of n and proportion. Note that only patients who underwent HSCT after the start of this drug will be included in this summary, except for "HSCT after the start of this drug [not performed, performed]":

- HSCT after the start of this drug [not performed, performed]
- Number of HSCTs after the start of this drug [1,  $\geq 2$ ]

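### Mortality after HSCT is to be estimated at Week 104 from the first HSCT, which planned follow-up in practice never reaches, and at Week 78, which no patient with a single HSCT reaches

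*SAP*

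**What the plan says.** **When observation ends.** Protocol 8.7 sets the observation period of transplanted patients to run "until 52 weeks following HSCT for patients undergoing it within 52 weeks after the start of BESPONSA treatment". It does not say which HSCT counts if there is more than one. SAP 2.1 settles this, with the start of the drug as the reference: "The starting point for the 52 week follow-up after HSCT is the day of the last HSCT performed within 52 weeks after the start". Repeat transplants are expected, since SAP 8.2.2 tabulates "Number of HSCTs after the start of this drug" as one or at least two.

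**How long survival is collected.** Protocol 8.8.12 collects survival information "from the start date of BESPONSA treatment to the end date of the observation period".

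**When the mortality clock starts.** SAP 6.1 counts time to death after HSCT as "Days and weeks from the date of first HSCT after the start of this drug to the date of death". Transplant-related and transplant-unrelated death have the same origin. For patients alive at completion or discontinuation of the survey, "The endpoint will be censored on the day when patient's survival was last confirmed".

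**When mortality is estimated.** SAP 8.2.3.3 lists Weeks 4, 8 and 12 and Day 100, and then "Week 24, Week 36, Week 48, Week 52, Week 78, and Week 104". The list applies to all three mortality endpoints, in transplanted patients of the safety analysis set who finished the survey.

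**The concern.** The end of observation is tied to the last qualifying HSCT, and the mortality clock to the first. For a patient with one HSCT the two coincide and planned follow-up is 52 weeks. The last two estimation times lie 26 and 52 weeks beyond that.

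A cumulative incidence curve is a step function: once nobody is left at risk, it stays at its last value. A Week 104 figure would then repeat an earlier estimate, or rest on a few patients with unplanned late survival dates. A Week 78 figure would rest on such dates or on re-transplanted patients, who are selected because they survived at least 26 weeks after the first HSCT and were then transplanted again. SAP 8.1.4 plans a rate at each time point but does not ask for the number at risk beside it. A reader of the final report could take the last row for two-year post-transplant mortality, which the design was not set up to observe.

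**Working it through.** The documents give no calculated figure for follow-up after HSCT, so there is none to reproduce. The check is date arithmetic.

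**Inputs.** Days are counted from drug start = 0.
- S = day of the first HSCT after drug start (origin of the mortality clock, SAP 6.1).
- L = day of the last HSCT within 52 weeks of drug start, so S ≤ L ≤ 52 × 7 = 364 (SAP 2.1).
- Planned end of observation = L + 364 (Protocol 8.7, SAP 2.1).

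**Planned follow-up from the first HSCT** = (L + 364) − S = 364 + (L − S).
- One HSCT: L = S, giving 364 days = Week 52.
- More than one: L ≤ 364, giving at most 728 − S days.

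**Week 104** = 104 × 7 = 728 days. This needs L − S ≥ 728 − 364 = 364. With L ≤ 364, the only solution is S = 0 and L = 364. Even a first HSCT on Day 1 stops at 727 days.

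**Week 78** = 78 × 7 = 546 days. This needs L − S ≥ 546 − 364 = 182 days (26 weeks). With L ≤ 364, S must be at most 182 (Week 26).

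| First HSCT | Longest planned follow-up from it (728 − S) | Re-transplant needed to reach Week 78 (L ≥ S + 182) |
|---|---|---|
| Week 8 (Day 56) | 672 days, Week 96 | Day 238 to 364 (Weeks 34–52) |
| Week 12 (Day 84) | 644 days, Week 92 | Day 266 to 364 (Weeks 38–52) |
| Week 16 (Day 112) | 616 days, Week 88 | Day 294 to 364 (Weeks 42–52) |
| Week 26 (Day 182) | 546 days, Week 78 | Day 364 only |
| Week 28 (Day 196) | 532 days, Week 76 | Day 378, outside the window |

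SAP 8.2.2 has a category for a first HSCT at 28 weeks or later. No patient in it has planned follow-up to Week 78.

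**Other time points.** Week 52 (364 days) is exactly the planned limit with one HSCT. Week 48 (336 days) and Day 100 are inside it.

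**Sensitivity to the reading of Protocol 8.7.** If the HSCT meant there were the first, follow-up from it would be 364 days for everyone, and Week 78 would also be out of reach for all. The SAP reading used above is the more generous one.

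**The case against.** **Later survival dates may exist.** Case report forms are completed afterwards: "The investigator will complete CRFs within the investigation period after the end of the observation period for each booklet". SAP 6.1 censors at the last confirmed survival with no cap at the planned end of observation, so a patient checked late could be at risk at Week 78 or 104. The revision history says the mortality time points were added in SAP version 4.0 of 28 October 2022. The last eligible start was 30 April 2020, and 728 days later is 28 April 2022, so planned observation had already ended. Actual follow-up might have guided the choice. This stands as a limit: a reader might infer that the late rows must be empty, and the documents do not support that. They do not say that late dates exist or how many, so the Week 104 row still has no planned support.

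**Numbers still followed are already planned.** SAP 8.2.1 counts patients followed after the first HSCT every 13 weeks, which includes Weeks 52, 78 and 104 (13 × 4, 13 × 6, 13 × 8). This helps a careful reader. But it is a separate table, it covers all transplanted patients in the set, and SAP 6.3 runs follow-up to the end date of the survey. The mortality analysis takes only patients who finished the survey and censors at last confirmed survival. The counts are not its risk set and do not qualify its rows.

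**Nothing is decided on these rows.** SAP 4.1 treats p-values as descriptive, SAP 4.2 has no decision rules, and early death is defined at 100 days. This stands and fixes the severity as minor.

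**Stronger readings to avoid.** A reader might infer that overall survival at Month 24 has the same fault. It does not: that clock starts at drug start, where the limit is 52 + 52 weeks = 728 days. Month 24 is Day 720 with 30-day months and Day 730–731 with calendar months, a matter of 2–3 days and of an undefined month length. A reader might also take the Week 52 stop in the VOD/SOS onset analysis as the SAP's own precedent. That analysis is timed from the start of treatment, and VOD/SOS in transplanted patients is collected until 52 weeks after the last HSCT, so Week 52 is not the end of their follow-up there.

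**Conclusion.** The point holds, as a minor error in a descriptive analysis. Week 104 from the first HSCT is in practice beyond planned follow-up for every patient. Week 78 is beyond it for every patient with one HSCT, by 546 − 364 = 182 days. Otherwise Week 78 is reachable only with a first HSCT by Week 26 and a re-transplant at least 26 weeks later, by Week 52. Week 52 is at the limit for patients with one HSCT and should be read with its number at risk. Early death within 100 days and the estimates through Week 48 are inside planned follow-up.

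The conclusion rests on the SAP's rule that the last HSCT by Week 52 starts the 52 weeks. It concerns planned follow-up only. How many patients were re-transplanted late, or had survival confirmed after the planned end, cannot be known from the documents.

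**What to change.** In SAP 8.2.3.3, Mortality after HSCT:

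- Delete Week 104, so that the list ends with Weeks 48, 52 and 78.
- Print the number at risk beside the Week 52 and Week 78 estimates, for all three mortality endpoints.
- Add a note: Week 78 is beyond planned follow-up for patients with one HSCT, and the estimate rests on re-transplanted patients or on survival dates confirmed later than planned.

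Deleting Week 78 as well is an acceptable alternative.

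The cost is a change of SAP wording and added numbers at risk in the mortality table. The downside is that one or two late time points are no longer tabulated. The curves remain and no data are discarded.
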